10.2 Analysis sets

During the phase I portion of the study. All patients who are evaluable for DLTs will be counted and used in the decision of dose escalation, expansion, de-escalation, and stopping. Patients who are inevaluable for DLTs will be replaced. However, all eligible patients who start treatment with study drugs will be counted in patient description. During the phase II portion of the study, all patients who start treatment with study drugs will be included. All patients need scan at the end of their study period to be counted for endpoints.

10.3 Statistical and analytical plans

Description analysis will be performed for both phase I and phase II parts of the study in terms of baseline demographic and disease characteristics and prior treatment. All DLTs will be listed by dose level. Toxicities that are not qualified as DLTs will be summarized by dose level, cycle, type, grade, and attribution to study drugs. Treatment cycles will be summarized by dose level.

Kaplan Meier curves will be used to show PFS and OS. Medians and probabilities of PFS and OS at 3 and 6 months and their 95%CI confidence intervals will be given. Response rate (CR or PR) will be calculated among patients during the phase II portion of the study for calculation of disease control rate (CR+PR+SD). All patients who are counted during that portion will be included in the denominator.

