--	---

	
ratio from a random urine sample (\geqGrade 3, NCI-CTCAE v 5.0).
 
 • Known hypersensitivity to any of the study drugs, study drug classes, or excipients in the formulation. • Major surgical procedure or significant traumatic injury within 28 days before start of study medication. • Non-healing wound, non-healing ulcer, or non-healing bone fracture • Patients with evidence or history of any bleeding diathesis, irrespective of severity • Any hemorrhage or bleeding event \geq CTCAE Grade 3 within 4 weeks prior to the start of study medication • Women who are pregnant or breastfeeding, or with the potential for pregnancy unwilling to undergo contraception. • Has a diagnosis of immunodeficiency or is receiving chronic systemic steroid therapy (in dosing exceeding 10 mg daily of prednisone equivalent) or any other form of immunosuppressive therapy within 7 days prior to the first dose of study drug. • Has an active infection requiring systemic therapy. • MSI colorectal cancers are not candidate for enrollment on this trial.
Study design	
Phase I is a standard 3+3 design evaluating escalating doses of regorafenib in combination with fixed dose pembrolizumab. The primary endpoint is to identify the recommended dose (RD) of the combination.
 
The phase II is an open label single arm study to assess the preliminary efficacy and tolerability of the combination therapy at RD in colorectal cancer patients who had failed standard therapy. The primary endpoint is PFS, we assume that combination therapy will result in prolongation of progression free survival by 50% compared to historical PFS with single agent regorafenib. Given that PFS in CORRECT trial was 1.9 mos with type one error of 10%, power of 80% we will need a sample size of 63 pts. The expected PFS in the treatment group will be 2.85 months. The accrual is expected to happen over 24 months. Tolerability will be assessed by median duration of treatment; combination is defined to be tolerable if the median duration of treatment is at least 20% better than CORRECT data (1.7 months).

Type of control	This study has no control
Number of subjects	A total of 3-18 patients will be enrolled and treated on the phase I. A total of 69 patients will be enrolled on the phase II portions of this trial. Six patients who are treated at MTD/RP2D of the phase I portion of the study will be counted for the phase II portion of the study too.

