We propose to combine regorafenib and PD1 (pembrolizumab) in colorectal cancer patients in 3rd and 4th line setting. Using a phase I/II design, we will first enroll 3-18 patient on phase I to find the recommended dose for phase II. We will then accrue patients to the phase II portion of the trial with the primary efficacy endpoint of PFS. An extensive biomarker analysis, liquid biopsies and tumor tissue, is planned to identify the population who would most benefit from this combination.

Four patients on dose level 1: 80mg were reviewed by the Phase I DLT Committee. One patient was deemed inevaluable for DLT and was replaced. Three patients were evaluable with no DLT. The trial was recommended to proceed to accrue three patients to dose level 2: 120mg. All three patients at this dose level had either grade 2 or grade 3 rash which required a dose reduction at either cycle 2 or 3. It was determined that the dose level 2: 120mg would

be challenging due to its overall tolerability; therefore, dose level 1: 80mg was recommended to expand and enroll additional three patients for a total of 6 patients to be reviewed.

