 - Grade 3 dermatologic toxicity (HFSR and non-life threatening events) for ≥ 7 consecutive days;
 - Grade 4 dermatologic toxicity of any duration;
 - \geq Grade 3 immune-related adverse events lasting for ≥ 8 consecutive days despite steroid therapy.

• Combination therapy:

When 70% of the planned regorafenib dose cannot be administered because of toxicity other than DLT during the DLT evaluation period it will be considered DLT. This criteria is in place to ensure the combination can be delivered safely.

Maximum Tolerated Dose (MTD)

During the Phase I portion, the maximum tolerated dose (MTD) is defined as the highest dose tested in which none or only one patient experienced DLT, when at least 6 patients were treated at that dose and are evaluable for toxicity. The MTD is one dose level below the lowest dose tested in which 2 or more patients experienced DLT, unless dose level 3 is established as the MTD. At least 6 patients will be treated at the MTD.

Numbers of Patients and Rules for Dose Escalation

Rules for dose escalation and expansion in cohorts of patients are based on DLT occurring in each patient's first cycle of treatment (21 days without delay or interruption). The standard 3+3 rules will be used. Three patients will be treated at each new dose level. If 0/3 patients experience DLT, 3 patients will be treated at the next dose level. If DLT is experienced in exactly 1/3 patients, 3 more patients (for a total of 6) will be treated at that dose level. If no additional DLT is observed at the expanded dose level (i.e. 1/6 with DLT), the dose will be escalated. Escalation will terminate as soon as two or more patients experience any DLT at a given dose level. The Phase I trial will be closed when 6 patients have been treated at the next lower

dose level, and at most 1/6 patients experience DLT. If more than 1/6 patients experience DLT, the next lower dose will be expanded.

All patients who have not experienced any DLT must be observed for a minimum of 3 weeks after the start of the first cycle, before the dose level is escalated.

There will be no dose escalation within a patient.

Toxicities of interest for Pembrolizumab

- Pneumonitis
- Hepatitis
- Colitis
- Hypothyroidism
- Hypophysitis

Miscellaneous

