7.3 Safety

All subjects who receive at least one dose of study treatment will be valid for the safety analysis.

All observations pertinent to the safety of the study treatment will be recorded and included in the final report.

Safety variables include the following: AEs, laboratory changes (complete blood counts, electrolytes, chemistry, and coagulation), changes in vital signs (blood pressure, heart rate, respiratory rate, and temperature) and ECG and, in some instances, changes in chest x-ray images, as produced at the investigator's discretion (e.g., for evaluation for pneumonia).

All AEs whether considered drug-related or not, will be reported in with a diagnosis, start/stop dates, action taken, whether treatment was discontinued, any corrective measures taken, outcome, and other possible causes. For all events, the relationship to treatment and the intensity of the event will be determined by the investigator.

This trial will use the NCI-CTCAE v5.0 criteria for assessment of toxicity and SAE reporting with regard to toxicity grade.

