- Expression of PDL1. PD-1 expression in tumor tissue.³³ MHC class I and II expression at baseline (archival tissue) and in collaboration with Merck.
- Additionally, archival tumor tissue will be obtained for NGS and correlation between CMS classification, mutational load, and immune scoring and treatment benefit.

Blood:

- A panel of proprietary biomarkers (SNPs in angiogenic and immune pathways) developed at [name] lab will be used for assessment of toxicity and efficacy.
- We intend to look at the global markers of immune activation by screening PBMC for: CD3, CD4, CD8, CD25, FoxP3, HLA-DR, ICOS1, CTLA-4, CD45RO, CD45RA, CD27, PD-1, CCR7, CD 62L, CD 69, ICOS, CD 95, CD127 and CD137 for analysis

by multi-color flow cytometry to phenotype and quantify the changes in immune markers following treatment on both CD4⁺ helper T cells, regulatory T cells and CD8⁺ cytotoxic T cells. Specifically the following sets of antibodies will be informative to the function of the T cells: CD45RA/CCR7/CD62L (naïve vs memory), FoxP3/CD25/CD127/CTLA-4 (nTreg), CD69/ICOS/PD-1/CD95 (activation vs exhaustion).

- Additionally, will collect CTC, cell free RNA and DNA at baseline and at progression for analysis of expression of MHC class I and II expression, and mutational load.

10. Statistical methods and determination of sample size

This is an open label single institution phase I/II with combination of regorafenib and pembrolizumab in patients with advanced colorectal cancer who have progressed or not tolerated standard therapies.

End points:

- Phase I: Dose limiting toxicity during the first course of therapy.
- Phase II: Progression-free survival (PFS), defined from the start of treatment (day 1 of cycle 1) to the time of disease progression or death from any cause whichever is sooner. Patients will be considered evaluable for PFS if they have received at least one dose of treatment and have at least one post baseline tumor assessment.
- Phase II: Overall survival, defined as the time from the start of treatment (day 1 of cycle 1) to death from any cause.

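### The only toxicity summary by type and grade in section 10.3 excludes DLTs, so it is not a full incidence table (at most one patient missing at the recommended dose)

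*Combined protocol and SAP*

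**What the plan says.** Section 10.3 gives two instructions on toxicity. For DLTs: "All DLTs will be listed by dose level". For everything else: "Toxicities that are not qualified as DLTs will be summarized by dose level, cycle, type, grade, and attribution to study drugs".

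Three other places bear on how these are read.

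- Section 7.3 sets the safety population: "All subjects who receive at least one dose of study treatment will be valid for the safety analysis". It also requires all safety observations to appear in the final report, but it defines no tabulation.
- The endpoint list that opens section 10 makes the phase I endpoint "Dose limiting toxicity during the first course of therapy". Section 6.2 bases the escalation rules on DLTs in each patient's first 21-day cycle.
- Section 10.4 provides monthly toxicity monitoring with reports to the principal investigator and the DSMC, again without specifying a table.

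No section specifies a summary by type and grade that combines DLTs with other toxicities.

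**The concern.** The wording of section 10.3 is an explicit exclusion. A programmer who follows it removes every DLT from the one table that shows cycle, type, grade and attribution. The DLT listing is specified by dose level only.

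The removal depends on how bad the event was, because nearly all DLT criteria in section 6.2 are thresholds of grade or duration. The table therefore tends to lose the worst first-cycle events and keep the milder ones of the same type. A proportion read from it is not the proportion of treated patients who had that toxicity.

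Safety of the combination is the stated phase I objective (section 2.1). Section 10.1 also counts six patients treated at the recommended dose in phase II, so a DLT in one of them would be missing from a pooled recommended-dose table as well. A reader wanting the full incidence would have to add the listing to the table by hand.

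**Working it through.** **Which events leave the table.** The DLT definitions in section 6.2, set against the exclusion in section 10.3, give this for phase I, cycle 1:

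| Event | DLT? | In the 10.3 summary? |
|---|---|---|
| Grade 3 skin toxicity, under 7 days | No | Yes |
| Grade 3 skin toxicity, 7 or more consecutive days | Yes | No |
| Grade 4 skin toxicity, any duration | Yes | No |
| ALT/AST 5–8 × ULN, bilirubin below 2 × ULN, ALT/AST below 5 × ULN within 7 days | No | Yes |
| ALT/AST above 8 × ULN | Yes | No |

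The skin criterion reads "Grade 3 dermatologic toxicity (HFSR and non-life threatening events) for ≥ 7 consecutive days". One DLT criterion, failure to deliver 70% of the planned regorafenib dose because of toxicity, has no grade threshold. Severe events in later cycles or in patients entering at phase II are outside the DLT definition and stay in the table.

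**How many patients can be missing at the recommended dose.** Section 6.2 defines the MTD as the "highest dose tested in which none or only one patient experienced DLT", with at least 6 evaluable patients treated. The closing rule in the same section also allows at most 1 of 6. The two agree: maximum patients with a DLT at the MTD = 1.

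**Size for one event type.** The understatement is (patients with a DLT of that type) / (denominator), with a numerator of 0 or 1.

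- Phase I cohort, 6 patients: 1/6 = 16.7 percentage points.
- Phase I cohort, 7 treated: 1/7 = 14.3 points. Section 1.1 reports four patients reviewed at 80 mg, one of them inevaluable for DLT, and three more to be added, so 4 + 3 = 7. This assumes that the inevaluable patient was dosed and is counted.
- Phase II set, 63 patients (section 10.1): 1/63 = 1.6 points.
- Phase II set, 69 patients (synopsis: "A total of 69 patients will be enrolled on the phase II portions of this trial"): 1/69 = 1.4 points.
- No DLT: 0. For 80 mg, section 1.1 so far reports "Three patients were evaluable with no DLT".

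**Effect on an interval.** If an event type occurred only as that one DLT, the table would show 0 instead of 1. The exact (Clopper–Pearson) 95% intervals are:

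| n | Shown as 0/n | Correct as 1/n |
|---|---|---|
| 6 | 0 to 45.9% | 0.4 to 64.1% |
| 63 | 0 to 5.7% | 0.04 to 8.5% |
| 69 | 0 to 5.2% | 0.04 to 7.8% |

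**The case against.** The strongest reply is that nothing is lost. The two sentences in section 10.3 together cover every toxicity: DLTs are listed and the rest are summarized. For a single patient a listing can tell the reader more than a table cell. Section 7.3 requires all adverse events to be reported with diagnosis, dates, action taken and outcome, with intensity and relationship to treatment judged by the investigator, and it sends all safety observations to the final report. The listing is not said to omit type, grade or attribution. Section 10.3 does not call its summary an incidence table. DLTs drive the dose decision, and phase II tolerability is judged on median treatment duration, so no decision uses this table. The rash at 120 mg described in section 1.1 led to dose reductions at cycle 2 or 3 and is not called a DLT, so no actual omission has been shown.

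Most of this stands. The data are collected, DLTs will be visible, and the consequence is confined to reporting. But requiring that observations appear in the report does not override a sentence that tells the analyst to leave DLTs out of the summary. A listing beside a truncated table is still not an incidence in all treated patients. Because the exclusion is stated, it cannot be put down to missing table shells.

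**Conclusion.** The point holds as a minor reporting fault. Followed literally, section 10.3 produces no table giving the full incidence of toxicity by type and grade in the section 7.3 safety population, and the events left out tend to be the more severe or longer-lasting ones.

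At the recommended dose the shortfall is at most one patient per event type, and possibly none. That bound rests on three conditions: the recommended dose meets the section 6.2 MTD rule, DLT is confined to phase I cycle 1, and patients are counted rather than events (one patient could have several DLTs). It does not cover a higher dose dropped for toxicity, where two or more patients could be left out of the table. The PFS sample size, type I error and power are unaffected, as is dose selection.

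**What to change.** In section 10.3, replace the sentence on non-DLT toxicities with: *All toxicities, including DLTs, will be summarized by dose level, cycle, type, worst grade per patient and attribution in all treated patients; DLTs will in addition be listed by dose level.*

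The cost is one sentence. It needs no new data or visits, and the DLT listing is kept.

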10.4 Planned interim analyses

There is no planned interim analysis for efficacy during the phase II portion of the study. A safety monitoring plan is laid out to further assess tolerability of the combination of regorafenib and pembrolizumab at MTD/RP2D among the first 20 patients during the phase II portion of the study. Our statistician will monitor the data for toxicity monthly and provide reports to PI and DSMC for update.

10.5 Endpoints

PFS: PFS is defined from the start of treatment (day 1 of cycle 1) to the first observation of disease progression (initial RECIST 1.1 progression) or death whichever comes first. The patients who are alive and disease progression is not observed, PFS is censored at the date of the latest disease assessment.

OS: OS is defined from the start of treatment (day 1 of cycle 1) to death. The patients who are alive and OS is censored at the last date known to be alive.

11.Data handling and quality assurance

11.1 Data recording

It is the expectation that all data has source documentation available at the site. The site must implement processes to ensure this happens.

11.2 Monitoring

11.2.1 Adherence to Protocol/Per Patient: It is the responsibility of the USC Principal Investigator (PI) to ensure that patient recruitment and enrollment, treatment, follow-up for toxicities and response, and documentation and reporting at USC are all performed as specified in the protocol. When a study is opened at two or more institutions, the PI at each institution will assume the responsibilities for the day-to-day monitoring of the trial, as described below.

11.2.2 Day-to-Day Monitoring – Eligibility: At USC, the Study Coordinator will assist the Investigator in reviewing eligibility and will assemble the required source documents, and do a final review by completing an Eligibility Registration Worksheet. When a study is opened at two or more institutions, the PI at each institution will review the patient eligibility in accordance with that institution's policy. For all institutions, the Eligibility Registration Worksheet with a copy of Informed Consent and supporting source documents will be submitted to CISO QA via email or Fax for verification prior to registering the patient on study.

Multi-Site Registration:

All participants in the multi-site trial are subject to central registration, which is used for tracking study accrual, checking eligibility, and monitoring adequate participation of women and minorities. Subject registration will be conducted through the coordinating center at the NCCC-CISO. External sites will identify eligible subjects and verify enrollment availability with the MCC prior to consenting patients. The external site is required to notify the MCC of a new signed informed consent within 48 business hours and note the basic consent information on the screening log. A copy of the consent will accompany the complete eligibility packet for verification. The MCC will enter the patient, demographic, and consent information in the applicable USC database. The MCC will assign a study patient sequence ID and communicate this to the external site.

The Coordinating Center Program Hours are 8 am to 4 pm, Monday through Friday, based on the PST zone. The MCC will be closed on official government holidays unless otherwise indicated. The contact number for the MCC is [contact].

External sites will verify eligibility prior to submitting documents to the MCC for central registration. External sites must submit registration requests to the MCC at least one full business day prior to the planned treatment start date. Registration will require the external site to submit to the MCC all of the following:

- A completed registration form with patient demographics:
- Zip code
- Payor Source

- Age
- Sex
- Race
- Ethnicity
- Initials
- Date of Birth (DOB)
- A completed Eligibility Checklist signed by the investigator
- A copy of the most recently IRB-approved, patient signed informed consent form
- All required screening tests, within the time parameters specified by the protocol study calendar
- All other de-identified source documents needed to verify all points of eligibility
- Any On-Study forms for registration specified by protocol

These documents must be securely emailed to the MCC staff. With advance notice documents will also be accepted faxed to [contact]. The MCC will verify completeness of documents and confirm eligibility. The MCC will enter the registration information in the USC OnCore® database. The MCC will then fax or securely email the completed Registration Form with the assigned study sequence ID to the external site as confirmation of patient registration.

An external site must maintain a log of all subjects who sign informed consents. The log must also document an explanation for exclusion due to screen failure. The MCC will provide sites with a Patient Tracking Log at the time of site activation. In the event of screen failure, external sites must submit the Screen Failure form to the MCC within one business day of determining screen failure.

Participating sites are required to retain, in a confidential manner, sufficient information on each subject so that the subject may be contacted should the need arise.

All documents, investigative reports, or information relating to the patient are strictly confidential. Any patient specific reports (i.e. Pathology reports, MRI reports, Operative reports, etc.) submitted to the CISO-MCC must have the patient's full name and social security number redacted (blacked out) and the assigned CISO-MCC patient ID number, protocol number, and site number written in. Patient initials only may be included or retained for cross verification of identification.

A registration verification letter will be emailed (preferred) or faxed to the registering site within one working day for patients registered to CISO-MCC multi-site trials. Treatment may not be initiated until the site receives this faxed or emailed verification.

11.2.3 Day-to-Day Monitoring – Informed Consent: Prior to registering the patient on study, the Study Coordinator will review the informed consent, to ensure that the patient has signed and dated the most current IRB-approved form, and that the form has been signed and dated by the person obtaining the consent as well as appropriate witnesses. A copy of the ICF will also be provided to CISO QA for review. CISO SOP 3.3 will be followed.

11.2.4 Day-to-Day Monitoring – Treatment: The PI and co-investigators are responsible for ensuring that treatment is given per protocol. The Study Coordinator will review the treatment orders with the treating investigator. Regardless of who the treating

physician is, there will be only one responsible Study Coordinator for each study at each of the hospitals affiliated with the USC Norris Cancer Center. The treating investigator will review the status of each patient on-study, with the Study Coordinator and treating physicians, on an on-going basis. When a study is opened at two or more institutions, CISO QA will periodically audit medical records for the subjects on study at other institutions to ensure compliance and adherence to the protocol.

- 11.2.5 Data Management – Patient Charts:** When a study is opened at two or more institutions, the policy in place at each institution will be followed for maintaining medical and research related records. Such policies will be provided to the CISO QA prior to enrolling 1st patient. At USC, all written source documents not associated with the study research are maintained in the patient chart, which is stored in the Department of Medical Records at the appropriate hospital. At the Norris Hospital, the official medical record is the Electronic Patient File (EPF). Radiographical images are stored in the Department of Radiology and in an electronic system called Synapse. At Los Angeles County General Hospital the official medical record is called Affinity. These are the permanent, official documents for each patient on-study. A copy of the signed informed consent, physician's notes, orders, test results and pathology notes are maintained in the patients' hospital charts. It is the responsibility of the research staff to ensure that the patient chart contains the required documents and work closely with treating investigators to ensure all protocol-related assessments are carefully documented.
- 11.2.6 Data Management – Research Charts:** When a study is opened at two or more institutions, the policy in place at each institution will be followed for maintaining medical and research related records. Such policies will be provided to the CISO QA prior to enrolling 1st patient. At USC, to facilitate adherence to the protocol schedule and data management, research charts are created to collect copies of the relevant notes, orders and results that are in the Patient Chart. In Addition, all source documents related to the research, such as original informed consent forms, HIPAA Forms, AE assessment worksheets, disease response worksheets and NTFs are maintained in the Research Charts. Protocol calendars, worksheets, and checklists, are also kept in the research chart. These are maintained in the Clinical Investigation Support Office until the study is completed and the results are published and no further need is anticipated. These are then stored off-site. It is the responsibility of the Data Manager to ensure that the research chart contains all the required documents.
- 11.2.7 Data Management – Case Report Forms:** It is the responsibility of the Data Manager to complete the required case report forms. For in-house trials, case report forms are developed for each trial; these are used to finalize the data entry screens in the Cancer Center clinical trials database. It is the responsibility of the PI to review

the Off-Study Summary form which summarizes pertinent toxicity, response and adherence information, once the patient has completed treatment.

Principal investigator and the study team at USC will have weekly safety meetings and conference calls during phase I period. These meetings will be held monthly, for the first 20 patients on phase II and if no unexpected signal of toxicity is observed the frequency of the meetings will be annual to correspond with the reporting period to DSMC. Furthermore, the opinion of the Data and Safety Monitoring Committee at USC can be sought as required on an ad hoc basis.

